Appendix 1: Signature of Investigator

Updated protocol title for consistency

August 21, 2019 Confidential 11 / 74

Synopsis

	·
Title:	A phase 1, multi-center, open-label, single-arm, dose-escalation, clinical study to evaluate the safety, tolerability, pharmacokinetics (PK) and anti-tumor activity of FN-1501 monotherapy in patients with advanced solid tumors or in relapsed/refractory Acute Myeloid Leukemia (AML)
Investigational drug:	FN-1501 lyophilized powder
Protocol No.	FN-1501-UP1
Clinical phase:	Phase 1
Number of patients:	Estimated 33 evaluable patients
Number of sites and locations:	3 sites in the United States (US) and Australia
Study cycle:	Screening period: Day -21 to Day -1. Treatment period: In the first cycle, a single dose of study drug will be administered three times a week on Days 1, 3, 5, 8, 10, and 12, with the last week off study drug (total 21 days). Subsequent treatment cycles will be 21 days and the study drug will be administered with the same dose and the same schedule as the first cycle. Follow-up period: 30 days after the last dose.
Objectives	
Primary	To evaluate the safety and tolerability of FN-1501 To determine the maximum tolerated dose (MTD) and recommended phase 2 dose (RP2D)
Secondary	To characterize the PK of FN-1501 and major metabolites To describe the preliminary anti-tumor activity of FN-1501

Study design:

This is a phase 1, first-in-human, open-label, multi-center, single-arm, dose escalation clinical study in patients with histologically or cytologically confirmed advanced solid tumors or relapsed/refractory AML, who cannot tolerate or do not respond to standard systemic therapy. It aims to determine the MTD and RP2D, evaluate the safety, tolerability, PK characteristics, and the preliminary anti-tumor activity of FN-1501.

August 21, 2019 Confidential 12 / 74

Eligible patients will receive a single intravenous infusion of study drug on Days 1, 3, 5, 8, 10, and 12 of a 21-day cycle. Dose limiting toxicity (DLT) assessment period is the first cycle of study treatment.

Starting dose, dose escalation scheme, and stopping criteria

- Dosing will begin at 2.5 mg once per day on the assigned days.

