4.1 Summary of Study Design

This is a phase 1, first-in-human, open-label, multi-center, single-arm, dose escalation clinical study in patients with histologically or cytologically confirmed advanced solid tumors or relapsed/refractory AML, who cannot tolerate or do not respond to standard systemic therapy.

Patients will be screened for eligibility for up to 21 days prior to entry into the study. The starting dose will be 2.5 mg/day on the assigned days. Dose escalation will use the traditional 3+3 design and follow a modified Fibonacci sequence until MTD is reached. Increments of 33% in the dose of FN-1501 will be undertaken after reaching 30 mg/day. Eligible patients will receive a single intravenous infusion of study drug on Days 1, 3, 5, 8, 10, and 12 of a 21-day cycle.

The DLT assessment period is 21 days from the first dose of FN-1501. Evaluation of a cohort of at least three (3) patients completing DLT assessment at any given dose level is required prior to determining the next dose level and dose regimen for the subsequent cohort.

August 21, 2019 Confidential 31 / 74

The highest dose under which one or no case of DLT is observed will be considered as MTD. If DLT cannot be observed, RP2D will be determined based on safety, preliminary anti-tumor activities and PK data.

Approximately thirty-three patients are expected to be enrolled.

After the first patient in the cohort receives the Cycle 1, Day 1 dose, subsequent patients in that cohort will not be dosed until the first patient has been evaluated for at least 48 hours to exclude unexpected acute toxicity. The continuous safety evaluation will be performed by investigators, the medical monitor, and the sponsor. A Safety Monitoring Committee (SMC) will determine dose levels to be administered and dose regimen during dose escalation based on the data available from the previous dose levels. If an MTD is not identified due to paucity of DLTs, the RP2D will be determined based on PKs, safety, tolerability, and preliminary efficacy.

If a patient wishes to continuously receive study treatment on completion of Cycle 1, the patient can continue study treatment in 21-day Cycle 2 and subsequent cycles (same as Cycle 2, all of 21 days' duration), defined as administration of 3 times per week for 2 weeks followed by 1 week rest, at the discretion of the investigator.

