4.1.1 Dose Escalation

The DLT assessment period is 21 days starting from the first dose of FN-1501. The study will follow a standard 3+3 dose escalation scheme and a modified Fibonacci sequence until the MTD is reached. Increments of 33% in the dose of FN-1501 will be undertaken after reaching 30 mg/day. Because of the dosage form (10 mg/vial), each dose will be rounded to numbers such as 2.5, 5, 10, 15, 22.5 mg/day, etc. At least three (3) patients will be enrolled into each cohort.

Additional patient(s), up to a maximum of four (4) patients in total, may be enrolled in a cohort if more than three (3) have been screened and are eligible for the cohort.

The DLT assessment and dose-escalation scheme will follow the same principle as stipulated for a standard 3+3 dose escalation design. For example, one (1) to three (3) additional patients will be enrolled if a DLT is observed in one (1) of first three (3) patients. No additional patients are required if a DLT is observed in one (1) of six (6) patients.

The starting dose will be 2.5 mg/day administered on the assigned days. One possible dose escalation scheme is presented in Table 1. Other dose levels may be evaluated during the study, depending on emerging data.

August 21, 2019 Confidential 32 / 74

Table 1: Suggested Dose Escalation Scheme

Dose Level/Cohort	Dose (mg/d)	Increase (%)
1	2.5	100
2	5	100
3	10	50
4	15	50
5	22.5	33
6	30*	33
7	40*	33

The actual dose levels and dose regimens administered in each step will depend on the data available from the previous level, as determined by the Safety Monitoring Committee.

As currently planned, if none (0) of the patients in one cohort experience DLT during the DLT assessment period, the dose to be administered in the next cohort will be increased by up to 100% (up to the 10 mg/d dose), by up to 50% (for the 10 mg and 22.5 mg doses) and by 33% thereafter, as determined by the SMC formed by the medical monitor, investigator, and sponsor representative.

The dose intervals will follow standard 3+3 escalation rules starting with the treatment of 3 patients as follows:

- 1. If 0 of 3 patients experiences a DLT, dose escalation will proceed to the next higher dose level at which 3 patients (up to 4) will be enrolled.
- 2. If 1 of 3 patients experiences a DLT, 3 more patients will be enrolled at the same dose level.
- 3. Escalation will continue if 0 or 1 of 6 patients experiences a DLT.

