- 4. If 2 or more patients in any dose level experience a DLT, dosing will stop.

No additional patients will be treated at a given dose level if two (2) or more of the patients in the cohort develop a DLT during the DLT assessment period. In this instance, the MTD is considered to have been exceeded. If the MTD is exceeded, the next lower dose level is considered MTD. Depending on the decision of the SMC and on review of available data, an additional intermediate

August 21, 2019 Confidential 33 / 74

^{*} Increments of 33% in the dose of FN-1501 will be undertaken after reaching 30 mg/day until the MTD is reached.

dose level, between the MTD-exceeding dose level and the next lower dose level, may be explored. If an MTD is not identified due to paucity of DLTs, the RP2D will be determined based on PKs, safety, tolerability, and preliminary efficacy.

DLT Definition:

DLT is any AE not attributable to disease or disease-related processes that occur during the DLT assessment period. DLT is determined by investigators based on NCI-CTCAE Version 4.03:

Non-hematologic:

- Grade 3 or greater nausea, vomiting and diarrhea despite optimal supportive care
- Any other clinically relevant ≥ Grade 3 non-hematologic toxicity (excluding asymptomatic biochemical abnormalities that are not clinically significant and resolve to Grade 2 or less in <7 days)
- Persistent Grade 2 toxicity such as nausea, vomiting, or fatigue despite optimal standard medical therapy that, in the opinion of the investigator, prevents continuous dosing
- Any toxicity which in the judgment of the investigator or sponsor is dose limiting

Hematologic:

- Grade 4 neutropenia lasting > 7 days
- Grade 3 Febrile neutropenia (defined as absolute neutrophil count [ANC] < 1000/mm³ with a single temperature of 38.3°C or a sustained temperature of 38°C for > 1 hour)
- Grade 3 neutropenic infection
- Grade 3 thrombocytopenia with bleeding
- Grade 4 thrombocytopenia

For elevations in hepatic function enzymes, DLT is defined as follows:

- Grade 4 aspartate aminotransferase (AST) or alanine aminotransferase (ALT) increase
- AST or ALT > 5 × upper limit of normal (ULN) if accompanied by ≥ Grade 2 elevation in bilirubin
- AST or ALT > 5 × ULN lasting > 3 days in patients without liver metastases

August 21, 2019 Confidential 34 / 74

• AST or ALT > 5 × ULN lasting > 3 days if the baseline value was ≤ 3 × ULN in patients with liver metastases

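### Section 4.1.1 does not say how a toxicity that starts in the 21-day DLT window but meets its duration criterion later is counted, or whether escalation waits for it

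*Protocol*

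**What the plan says.** **Window.** Section 4.1.1: "The DLT assessment period is 21 days starting from the first dose of FN-1501". Doses are given "on Days 1, 3, 5, 8, 10, and 12 of a 21-day cycle" (Section 4.1), and the Synopsis describes the cycle "with the last week off study drug (total 21 days", so Days 15-21 are the rest week.

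**What counts.** The DLT definition in Section 4.1.1 opens: "DLT is any AE not attributable to disease or disease-related processes that occur during the DLT assessment period".

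**Criteria that need a duration (solid tumors).** There are four:
- "Grade 4 neutropenia lasting > 7 days"
- "AST or ALT > 5 × ULN lasting > 3 days in patients without liver metastases"
- "AST or ALT > 5 × ULN lasting > 3 days if the baseline value was ≤ 3 × ULN", for patients with liver metastases
- AST or ALT above 8 × ULN for more than 3 days, for liver metastases with a higher baseline value

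**AML haematologic criterion.** Prolonged Grade 4 neutropenia or thrombocytopenia without leukemia, judged at least 42 days after Cycle 1 begins.

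**Escalation.** Section 4.1 sets a minimum before a further level is chosen: "Evaluation of a cohort of at least three (3) patients completing DLT assessment at any given dose level is required prior to determining". In Section 4.1.1, numbered rule 1 escalates on 0 of 3. A cohort may hold four patients. The paragraph before the numbered rules escalates when no patient in the cohort experiences a DLT during the assessment period. The paragraph after them closes a level when two or more patients develop a DLT during that period.

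**The concern.** The definition ties the window to the adverse event. The escalation and stopping sentences tie it to the DLT. For a toxicity that becomes a DLT only after several days these are different dates, and the text does not say which one governs. The same patient can be a DLT under one sentence and DLT-free under another.

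The escalation gate does not remove the ambiguity. It asks for three completers and does not mention an event still running at Day 21, or a fourth patient still inside the window.

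The MTD is a primary objective of this first-in-human trial. With three to six patients per level, one reclassified patient can turn a decision to expand or stop into a decision to escalate.

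**Working it through.** **1. The plan's own figure.** Section 10.1 gives about 33 patients: three cohorts of 3 plus four cohorts of 6 = 9 + 24 = 33. It reproduces. The point below does not depend on it.

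**2. Latest onset that completes its duration by the end of the window.** More than d days is taken as d + 1 days. Let W be the last day considered.
- Counting calendar days inclusively: latest onset = W − (d + 1) + 1.
- Counting elapsed days: latest onset = W − (d + 1).

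| W | Neutropenia, d = 7 | AST/ALT, d = 3 |
|---|---|---|
| 21 (end of window) | Day 13-14 | Day 17-18 |
| 25 (latest end-of-period visit) | Day 17-18 | Day 21-22 |

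W = 25 comes from Table 2, footnote 2: the end-of-period assessments fall on Cycle 2 Day 1 (nominally Day 22) ± 3 days, that is Days 19-25.

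So a Grade 4 neutropenia that starts anywhere in the rest week is undecided at Day 21. An AST/ALT rise is undecided only if it starts on about Days 18-19 to 21. Neutropenia starting on Day 21 is settled on about Day 28-29, roughly one week after the window closes.

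**3. AML.** 42 − 21 = 21. The haematologic criterion cannot be judged until three weeks after the window closes.

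**4. When such an event would be seen.** Table 2 schedules Cycle 1 hematology and chemistry on Days 1 and 8, and next on Cycle 2 Day 1 (Days 19-25). After the Day 8, 10 and 12 doses, the first scheduled blood count falls around the close of the window. A neutropenia first found there has unknown onset and unproven duration.

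**5. Direction and possible size.** Under 3+3 with true DLT probability p per patient, ignoring the option of a fourth patient:

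P(escalate) = (1 − p)³ + 3p(1 − p)² × (1 − p)³

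If a share f of DLTs goes uncounted, p becomes p(1 − f). Both p = 0.33 and the values of f are assumptions; the protocol gives neither.

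| f | p(1 − f) | P(escalate) |
|---|---|---|
| 0 | 0.330 | 0.434 |
| 0.10 | 0.297 | 0.500 |
| 0.20 | 0.264 | 0.570 |
| 0.33 | 0.221 | 0.663 |

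For f = 0: 0.67³ = 0.301, and 3 × 0.33 × 0.67² × 0.67³ = 0.134; the sum, before rounding of the terms, is 0.434.

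**6. Fourth patient.** At the same assumed rate, the chance that the first three are clear and a pending fourth then has a DLT is 0.67³ × 0.33 = 0.099.

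**The case against.** The strongest reply is that the definition speaks of an adverse event occurring in the window and nowhere requires its duration to be completed there. Read that way, neutropenia starting on Day 18 counts once it has lasted long enough.

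Other text also protects:
- The investigator or sponsor may call any toxicity dose limiting, with no duration attached.
- Febrile neutropenia, Grade 4 thrombocytopenia and Grade 4 AST/ALT need no duration.
- Abnormal counts are repeated until they resolve, as often as the investigator thinks necessary (Table 2, footnote 9; Section 7.1.1).
- Section 5.2.1 withholds drug from a patient with a Grade 3 or higher event.
- The Safety Monitoring Committee decides each step and is not compelled to treat an ongoing Grade 4 event as no DLT.
- The sentence on no patient in the cohort having a DLT reaches a fourth patient.

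Much of this stands, and it rules out several stronger readings that a reader might infer:
- *Rest-week events can never qualify.* The onset reading allows them. Even on the strict reading, AST/ALT rises starting on Day 15 to 17-18 finish in time.
- *The allowance for asymptomatic biochemical abnormalities resolving in under 7 days adds to the under-count.* It is an exclusion from DLT. An abnormality not yet shown to resolve is not excused by it.
- *Section 4.2.4.1 makes 21 days without withdrawal equal to DLT-free.* It defines patient completion, which also needs a valid PK profile. It is not a scoring rule.
- *Late neutropenia is the expected pattern.* Section 1.3 reports decreased blood cell counts in rats and monkeys without their timing.

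The onset reading still does not settle the matter. The escalation and stopping sentences place the DLT itself inside the window, and no sentence makes the escalation decision wait for an open event. Discretion may catch such cases, but it is not a counting rule.

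**Conclusion.** The concern holds as an ambiguity with a safety direction. Sections 4.1 and 4.1.1 give no single answer for a solid-tumor event that is undecided at Day 21. For AML, the 42-day criterion and the 21-day window are in plain conflict. On a literal reading of rule 1 and the three-completer minimum, escalation may proceed while an event or a fourth patient is unresolved, although the cohort-wide sentence points the other way.

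Any under-count can act in one direction only, toward escalation and a higher MTD. Its size is not known. The range 0.500 to 0.663 against 0.434 rests on an assumed true rate of 0.33, an assumed 10% to 33% of DLTs uncounted, independent patients and cohorts of three then six. If sites apply the onset reading and the committee waits for open events, the shift is nil. An upward-biased MTD is therefore a risk that the wording permits; the documents do not show that it occurs.

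**What to change.** Reconcile the DLT definition, the AML criterion, the escalation and stopping sentences and the numbered rules in Section 4.1.1 with the three-completer sentence in Section 4.1, so that one counting rule states:

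1. how an event is classified if it starts within the window and has neither met nor failed its duration criterion when the window closes;
2. how the AML haematologic criterion at 42 days or more relates to the 21-day window;
3. that a patient whose DLT status is open, including a fourth patient, is not counted as DLT-free when escalation is decided.

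Which thresholds, durations and time horizons are clinically right is for the sponsor and investigators. The change concerns counting only and leaves doses and toxicity grades as they are.

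The text costs a few sentences in an amendment. The price in time is about a week for an open solid-tumor event, and up to about 21 days for a late fourth patient or an open AML haematologic event.

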3.1 Primary Endpoints

The safety of FN-1501 will be assessed throughout the study by monitoring adverse events (AEs) and serious adverse events (SAEs) [per the National Cancer Institute-Common Terminology Criteria for Adverse Events (NCI-CTCAE) Version 4.3], physical examination, and laboratory measurements.

The MTD of FN-1501 will be the highest dose under which one or no case of dose limiting toxicity (DLT) is observed while the RP2D of FN-1501 will be determined based on PKs, safety and tolerability, as well as preliminary efficacy.

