• AST or ALT > 8 × ULN lasting > 3 days if the baseline value was > 3 × ULN but ≤ 5 × ULN in patients with liver metastases

Specific DLT definitions for patients with AML:

Non-hematologic:

• All non-hematologic toxicities NCI-CTCAE ≥ Grade 3

Hematologic:

Prolonged myelosuppression defined as persistence of ≥ Grade 4
neutropenia or thrombocytopenia in the absence of leukemia (blast count
<5%) at least 42 days after the initiation of Cycle 1

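### The AML haematologic DLT cannot be established before Day 42, but the DLT period is 21 days, and the protocol does not say whether the AML list replaces or adds to the general haematologic list

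*Protocol*

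**What the plan says.** **Window.** Section 4.1.1 states: "The DLT assessment period is 21 days starting from the first dose of FN-1501". The Synopsis (study design), Section 4.1, footnote 2 to Table 2 and Section 4.2.4.1 agree with it. No separate period is given for AML.

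**Definition.** Section 4.1.1: "DLT is any AE not attributable to disease or disease-related processes that occur during the DLT assessment period".

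**Decision point.** Section 4.1: "Evaluation of a cohort of at least three (3) patients completing DLT assessment at any given dose level is required" before the next dose level is chosen. The escalation sentence in Section 4.1.1 applies "if none (0) of the patients in one cohort experience DLT during the DLT assessment period".

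**AML list.** Under its AML heading, Section 4.1.1 gives one non-haematologic item (all toxicities of Grade 3 or higher) and one haematologic item: Grade 4 neutropenia or thrombocytopenia that persists, with a blast count below 5%, "at least 42 days after the initiation of Cycle 1". The list follows the general one, and nothing says whether it stands in place of it or beside it. The Version 3 amendment rationale says only that AML definitions were added.

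**General haematologic list.** This includes Grade 4 thrombocytopenia with no minimum duration. Section 4.2.1 exempts AML patients from the entry limits for platelets, neutrophils and haemoglobin.

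**MTD.** Section 3.1: "The MTD of FN-1501 will be the highest dose under which one or no case of dose limiting toxicity (DLT) is observed".

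**The concern.** Determining the MTD is a primary objective (Section 2.1). It turns on whether 0, 1 or 2 DLTs are seen among three to six patients, so one event classified differently can change a decision. For AML, the listed haematologic event cannot be established until after the period that defines a DLT has ended, and possibly after the cohort decision has been taken. Two teams following the same text could count that event differently.

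The silence on replacing or adding to the general list makes this worse, because the two readings pull the escalation decision in opposite directions.

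This is not detail for the statistical analysis plan. The protocol itself fixes these rules, and they are applied in real time.

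**Working it through.** **Timing.** 42 - 21 = 21 days. The AML item can be met no earlier than 21 days after the DLT period closes, that is, after two 21-day cycles rather than one. Cytopenia may begin in Cycle 1, but the criterion needs persistence to Day 42 or later.

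**The plan's own figure.** Section 10.1 expects about 33 patients: 3 cohorts x 3 + 4 cohorts x 6 = 9 + 24 = 33. This reproduces. It does not depend on the DLT window, so it neither supports nor weakens the point.

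**Reading A: the AML list replaces the general haematologic list.** No listed haematologic DLT can then be scored in an AML patient by Day 21. The protocol gives no DLT rates, so the following are assumptions for illustration:
- non-haematologic DLT 10% in both groups;
- haematologic DLT 30% in solid tumours;
- late AML criterion met in a proportion q;
- k AML patients in each set of three.

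Per-patient DLT probabilities:
- solid tumour: s = 1 - 0.9 x 0.7 = 0.37;
- AML, late criterion counted: a = 1 - 0.9 x (1 - q);
- AML, late criterion unread: a = 0.10.

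P(escalate) = P(0 of 3) + P(1 of 3) x P(0 of next 3).

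Worked case, k = 1, q = 0.10:
- Counted, a = 0.19. P(0) = 0.81 x 0.63² = 0.3215. P(1) = 0.19 x 0.3969 + 0.81 x 2 x 0.37 x 0.63 = 0.4530. P(escalate) = 0.3215 + 0.4530 x 0.3215 = 0.467.
- Never read, a = 0.10. P(0) = 0.90 x 0.3969 = 0.3572. P(1) = 0.0397 + 0.4196 = 0.4593. P(escalate) = 0.3572 + 0.4593 x 0.3572 = 0.521.
- Unread at the three-patient decision, but the first three patients' late events known at the six-patient decision. P(exactly one early DLT and no late event in the others) = 0.0397 + 0.4196 x 0.90 = 0.4173. P(escalate) = 0.3572 + 0.4173 x 0.3572 = 0.506.
- Bias: 0.506 - 0.467 = 0.039, to 0.521 - 0.467 = 0.054.

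The same steps for other cases:

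| q | AML of 3 | Counted | First three's late events known | Never read | Upward bias |
|---|---|---|---|---|---|
| 0.02 | 1 | 0.510 | 0.518 | 0.521 | 0.008-0.011 |
| 0.05 | 1 | 0.494 | 0.514 | 0.521 | 0.020-0.027 |
| 0.10 | 1 | 0.467 | 0.506 | 0.521 | 0.039-0.054 |
| 0.10 | 2 | 0.594 | 0.686 | 0.721 | 0.092-0.127 |
| 0.10 | 3 | 0.730 | 0.872 | 0.906 | 0.142-0.176 |
| 0.30 | 3 | 0.360 | 0.816 | 0.906 | 0.456-0.546 |

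The last row is an extreme. It needs an all-AML cohort and a high q, and q is limited because the criterion requires blasts below 5% in patients who entered with at least 20% (Section 4.2.1).

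**Reading B: the AML list adds to the general list.** Grade 4 thrombocytopenia of any duration is then a DLT in patients with no platelet minimum at entry, limited only by the exclusion of events attributable to disease. If a share b of AML patients were scored this way (b is assumed), then in an all-AML cohort P(2 or more of 3) = 3b²(1 - b) + b³. This gives 0.104, 0.352 and 0.648 for b = 0.2, 0.4 and 0.6. The pressure is towards stopping. The 42-day item still cannot be established by Day 21.

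**The case against.** **A late event can count.** A reader might infer that the 42-day item can never be a DLT under the protocol's own definition. The text does not support that. The definition asks that the event occur in the period, and cytopenia starting in Cycle 1 can be said to occur then and be confirmed later. What stands is narrower: it cannot be confirmed by Day 21, and the text neither adopts the onset reading nor says what a later confirmation does.

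**The timed and untimed rules.** Rule 4 ("If 2 or more patients in any dose level experience a DLT, dosing will stop") and the MTD definition carry no time limit, while the adjoining sentence counts cases where "two (2) or more of the patients in the cohort develop a DLT during the DLT assessment period". A reader might infer a general conflict. But both untimed rules use the term DLT, which Section 4.1.1 already confines to the period, so for ordinary DLTs they agree. The difference arises only for the 42-day AML item.

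**Replacement and marrow timing.** Section 5.4 permits replacement and Section 10.2.3 commits to it, where possible, for withdrawals within the period. These can coexist. The scheduled marrow can fall before Day 42 (6 weeks ± 5 days, Days 37 to 47), but extra marrows are allowed and a later one satisfies the criterion. Neither is a defect.

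**Safeguards.** Three patients completing assessment is a minimum, not an instruction to decide on Day 21. The Safety Monitoring Committee sets doses on available data (Sections 4.1 and 4.1.1), safety is evaluated continuously (Section 10.2.2), and non-haematologic AML DLTs remain scorable within 21 days. These soften the problem, but none states the AML window, the applicable list or the treatment of a late DLT.

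**Conclusion.** The point holds as an inconsistency in Section 4.1.1, and it must be fixed because it concerns the rule behind a primary objective. Three things are unsettled: when the AML haematologic criterion is read relative to the DLT period, which haematologic list applies to AML, and how a DLT confirmed after an escalation decision counts. None of these depends on an assumed rate.

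The size does. On the replacement reading, the upward bias in the chance of escalating ranges from about 0.01 (one AML patient of three, q = 0.02) to 0.14-0.18 (three of three, q = 0.10). These figures rest on assumed DLT rates, an assumed AML share and that reading alone. They concern one escalation step and are not an error rate for the MTD. A reader might infer that the plan systematically over-escalates. The documents do not support that, because the additive reading could push the other way. The direction is uncertain.

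**What to change.** - Reconcile Sections 4.1 and 4.1.1, footnote 2 to Table 2 and Section 4.2.4.1 (and the matching Synopsis sentence) so that the AML DLT window and the time at which the AML haematologic criterion is read agree.
- State whether the general haematologic list applies to AML patients.
- State how a DLT confirmed after an escalation decision counts for that decision and for the MTD (Sections 3.1, 4.1 and 4.1.1).
- Carry the reconciled window into completion and replacement (Sections 4.2.4.1, 4.2.4.2, 5.4 and 10.2.3).

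Which window or criterion is right is for the sponsor.

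The change is to wording only, but it may cost time. If the longer window is kept, decisions for cohorts with AML patients may come about 3 weeks later per three-patient reading (42 - 21 = 21 days), or about 6 weeks for a dose level expanded to six. A few replacements may be needed beyond the approximately 33 patients expected. Cohorts of solid-tumour patients only are unaffected.
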